9.3 Statistical Analyses

All baseline and demographic variables such as race, gender, age, height, and weight will be summarized. Continuous variables will be summarized using mean, standard deviation, median, IQR, minimum and maximum. Categorical variables will be presented using frequencies and percentages.

Difference in infected status proportions between the treatment and control groups will be evaluated using Fisher's exact test. The number of adverse events, rate of occurrence, and severity by treatment group will be reported and statistically compared using non-parametric methods.

Details of the analysis methods will be provided in the Statistical Analysis Plan (SAP), which will be finalized as early as possible after enrollment commences in order to minimize bias in the analysis strategy.

9.4 Interim Analysis

An interim analysis will be conducted to determine if the study should be stopped due to safety concerns or efficacy. Using O'Brien-Fleming approach, the interim analysis will use a significance level of $\alpha=0.0054$ and the final analysis will use a significance level of 0.0492. The interim safety analysis will be performed when 50% of subjects, within their respective cohort, complete their 35 day follow-up. Overall safety will be analyzed first, and if safety outcomes are statistically higher in the treatment group ($\alpha=0.0054$), enrollment will be stopped, participants will be unblinded and each cohort will be analyzed independently. If safety has not been compromised the study maybe resumed after review and recommendation by the SRC. Efficacy will be analyzed for early declaration of success. If power of 90% has been detected and a statistically significant change has been identified ($\alpha=0.0054$), that specific cohort will stop enrollment and the final analysis will be done with completed data from participants enrolled at that time, otherwise the study will continue enrolling patients and final analysis will be completed.

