9.2 Sample Size Determination

Cohort A:

It is expected that 10% of exposed healthcare workers will convert to infected status without intervention. The treatment arm will be assumed to have a conversion of 5% (50% relative reduction, 5% absolute risk reduction). Due to the uncertainty of this

trial, a conservative 10% drop out rate is included in the calculation. Under these assumptions (Treatment: 5% infected, Control: 10% infected, α : 0.0492, Power: 90%), the total sample size is 1356 patients (610 patients are needed in each arm + 10% dropout = 1356 total patients).

Cohort B:

It is expected that 30% of exposed high risk patients will convert to infected status without intervention. The treatment arm will be assumed to have a conversion of 15% (50% relative reduction, 15% absolute risk reduction). Due to the uncertainty of this trial, a conservative 10% drop out rate is included in the calculation. Under these assumptions (Treatment: 15% infected, Control: 30% infected, α : 0.0492, Power: 90%), the total sample size is 383 patients (172 patients are needed in each arm + 10% dropout = 383 total patients).

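### Do the O'Brien-Fleming levels 0.0054 and 0.0492 let the false-positive rate exceed 5%?

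*Combined protocol and SAP*

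**What the plan says.** Section 9.4 sets one interim analysis by an O'Brien-Fleming approach, with 0.0054 at the interim, "and the final analysis will use a significance level of 0.0492". The 50% timing is attached to safety: "The interim safety analysis will be performed when 50% of subjects, within their respective cohort, complete their 35 day follow-up". For efficacy the text says "Efficacy will be analyzed for early declaration of success", with no separate timing. The efficacy stopping rule opens "If power of 90% has been detected and a statistically significant change has been identified" (at 0.0054). If it is met, the cohort stops enrolling and "the final analysis will be done with completed data from participants enrolled at that time".

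Section 9.2 carries 0.0492 into both sample sizes: for Cohort A "610 patients are needed in each arm + 10% dropout = 1356 total patients", and for Cohort B "172 patients are needed in each arm + 10% dropout = 383 total patients".

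Section 9.3 names the efficacy test: "Difference in infected status proportions between the treatment and control groups will be evaluated using Fisher's exact test". It leaves further detail to a SAP that is to be finalised after enrolment begins. Sections 9.1 to 9.4 give neither an overall alpha nor the sidedness of the test.

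**The concern.** A reader who checks 0.0054/0.0492 against O'Brien-Fleming boundaries at the conventional two-sided 5% will not reproduce them. The pair has the right shape for a look at half information, but its constant is 1.967 where 1.977 is needed, so it appears to spend slightly more than 5%. These levels decide success in each cohort, and 0.0492 also feeds both sample sizes. An excess in the actual error rate would therefore matter for the claim and would call for changes in sections 9.2 and 9.4. The condition about detected power adds to the doubt, because it is undefined and could move the interim boundary.

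**Working it through.** **Inputs.** Levels 0.0054 and 0.0492 and the 50% timing (9.4); 5% v 10% with 610 per arm, 15% v 30% with 172 per arm, power 90%, dropout 10% (9.2); Fisher's exact test (9.3); 1:1 allocation (6.1). Assumed: overall target two-sided 5% per cohort, efficacy look at 50%, Fisher's test at both looks.

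**1. The plan's sample sizes.** Exact two-sided Fisher power at 0.0492 is 90.02% with 610 per arm and 90.04% with 172 per arm. With dropout, 1220/0.9 = 1355.6, giving 1356, and 344/0.9 = 382.2, giving 383. Section 9.2 reproduces exactly, which supports a two-sided reading. One-sided formulas give 476 to 516 and 132 to 145 per arm.

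**2. The pair in normal theory.** The two-sided z values are 2.782 and 1.967, with ratio 1.4145, or √2. This is the O'Brien-Fleming shape at half information. With correlation √0.5 between the looks,

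total = 1 − P(|Z1| < 2.782, |Z2| < 1.967) = 0.0513.

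Solving for a total of 0.0500 with bounds c√2 and c gives c = 1.9774, so z = 2.7965 and 1.9774, and levels 0.0052 and 0.0480.

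**3. How far 5.13% depends on reading the rule.**

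| Reading of the stated pair | Total |
|---|---|
| Every interim p ≤ 0.0054 is a rejection, look at 50% | 5.13% |
| Same, look at 40% / 60% | 5.20% / 5.06% |
| Observed power 90% at the final level also required (z ≥ 1.967 + 1.282, about 3.25) | 4.95% |
| Observed power 90% at the interim level also required (z ≥ 2.782 + 1.282 = 4.06) | 4.92% |
| Crossing must be confirmed at 0.0492 at 60% / 70% / 80% information | 5.11% / 5.06% / 5.00% |

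If the condition means conditional power under the current trend, it does not bind: that power is 99.7% at z = 2.782, so 5.13% stands. Under the two observed-power readings, 0.0052/0.0480 would total 4.83% or 4.80%, further from 5% than the stated pair.

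**4. Actual error with Fisher's test.** Full enumeration of both looks (305 then 610 per arm; 86 then 172 per arm), same infection rate in both arms:

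| Cohort and null rate | 0.0054/0.0492 | 0.0052/0.0480 |
|---|---|---|
| A, 5% | 3.70% | 3.62% |
| A, 10% | 4.05% | 4.03% |
| B, 15% | 3.49% | 3.49% |
| B, 30% | 3.93% | 3.75% |

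Over null rates from 1% to 50%, the maximum at the stated levels is 4.58% (A) and 4.07% (B).

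**5. What a switch would change.** Final-look Fisher power falls from 90.02% to 89.85% (A) and from 90.04% to 89.74% (B). At the final look, only a p-value between 0.0480 and 0.0492 changes status. Its probability is 0.02% (A) and 0.18% (B) under the null at 10% and 30%, and 0.17% and 0.30% under the design alternatives.

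**The case for a change.** The best case for a change is that protection comes from the test and not from the levels. Section 9.4 does not name the interim test. An uncorrected chi-square test at both looks would have an actual error of about 5.1% to 5.2% around the planning rates, so the levels ought to be right on their own terms. That arithmetic stands, but section 9.3 names Fisher's test for this comparison and the sample sizes reproduce under it. An analyst would use the same test at the interim.

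The second argument is that the power condition has no definition. With an interim z between 2.78 and 3.25, one statistician would stop the cohort and another would continue. The text also does not say whether a crossing is itself the rejection. This is a real gap in wording, and it is a stronger point than the third decimal of the levels. But the observed-power readings only tighten the interim boundary, the conditional-power reading leaves it where it is, and confirmation at 0.0492 only removes rejections. None of them takes the Fisher error above 5%. A SAP is still to come in which such details belong.

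**Conclusion.** No change is needed. On the strictest reading the stated pair exceeds a 5% target by 0.13 percentage points in normal theory, and the documents do not state that target. Under the planned Fisher's exact test the actual two-look error is about 3.5% to 4.1% at the planning rates. Moving to 0.0052/0.0480 would make a conservative test slightly more conservative and would unsettle sample-size figures that now agree with their stated power.

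This rests on two-sided testing, an efficacy look at half of each cohort, and Fisher's test at both looks. It concerns efficacy within one cohort and does not cover the safety comparison, which section 9.3 assigns to unspecified non-parametric methods. The overall alpha, the timing of the efficacy look and the meaning of the power condition are details that analysts can settle sensibly in the SAP without altering the levels or the sample sizes.

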8.2.2 Adverse Event (AE) Monitoring

The investigator or licensed designee (RN, CNP, pharmacist, or physician) on the study team will assess each participant to evaluate for potential new or worsening AEs as specified in the SoA and more frequently if clinically indicated. If participant reported symptoms are an AE, the event will be tracked as an AE.

Participants will be followed and accessed for acute AEs until day 35 (30 days after the last dose of study medication). AEs will be documented accordingly. Adverse events will also be assessed at the 12 month follow up visit.

8.3 Adverse events and Serious Adverse Events (SAE):

An AE is defined as any untoward or unfavorable medical occurrence in human participants, including any abnormal sign, symptom, or disease, temporally associated with the participant's participation in the research, whether considered related to the participant's participation in the research or not. AEs encompass both physical, psychological harms, and biochemical abnormalities. AEs may be reported by the participant, observed by the Investigator, or documented in medical records.

The site investigator and any licensed designees are responsible for detecting, documenting, and recording events that meet the definition of an AE or SAE and remain responsible for following up AEs that are serious, considered related to the study intervention or study procedures, or that caused the participant to discontinue the study treatment. The site investigator or licensed designee will evaluate all adverse events according to the National Cancer Institute (NCI) Common Terminology Criteria for Adverse Events (CTCAE) Version 5.0. Toxicities will be characterized in terms regarding grade (seriousness), causality/attribution (see section 8.3.2), and action taken with regard to trial intervention.

Any adverse event which changes CTCAE grade over the course of a given episode will have each change of grade recorded on the adverse event case report forms/worksheets.

If the adverse event meets any of the criteria below, it is regarded as a SAE:

- the event led to the death of the participant
- the event led to serious deterioration in the health of the participant, that either resulted in:
 - a life-threatening illness or injury
 - a permanent impairment of a body structure or a body function
 - in-patient or prolonged hospitalization

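### Does the undefined safety outcome in the interim stopping rule let COVID-19 illness mask drug-caused harm?

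*Combined protocol and SAP*

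**What the plan says.** Section 9.4 sets one interim look per cohort: "The interim safety analysis will be performed when 50% of subjects, within their respective cohort, complete their 35 day follow-up". Safety comes first: "Overall safety will be analyzed first, and if safety outcomes are statistically higher in the treatment group" at 0.0054, enrolment stops. The same look covers benefit: "Efficacy will be analyzed for early declaration of success". Section 9.4 names no event set, grade, unit of analysis or test for safety.

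Section 9.3 adds: "The number of adverse events, rate of occurrence, and severity by treatment group will be reported and statistically compared using non-parametric methods". It then defers: "Details of the analysis methods will be provided in the Statistical Analysis Plan (SAP". No such definition appears in the supplied text.

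The adverse event definition in section 8.3 is broad, "including any abnormal sign, symptom, or disease", whether or not related to participation. The serious-event criteria there include "in-patient or prolonged hospitalization". Section 8.2.2 is conditional: "If participant reported symptoms are an AE, the event will be tracked as an AE". No section exempts COVID-19.

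Other text points towards separation:
- Table 1 gives the COVID-19 outcome its own row, apart from adverse event assessment.
- Section 8.2.1 collects COVID-19 symptoms first and asks about other symptoms separately. Its sentence on inclusion in adverse event monitoring most naturally refers to the latter.
- Section 8.3.2 directs adverse event assessment at organ systems where toxicity is known to be possible, plus other toxicities the participant mentions.

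**The concern.** In a prophylaxis trial the efficacy endpoint is itself an illness. Section 9.2 assumes infection in 10% v 5% (Cohort A) and 30% v 15% (Cohort B), placebo first. Read literally, the adverse event definition covers symptomatic COVID-19, and a COVID-19 admission or death is a serious event reported whatever its attribution. If such events entered the section 9.4 comparison, a placebo excess of disease would offset a drug excess of toxicity. The test would then be least sensitive to harm exactly when the drug worked.

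The separation described above could also leak. Section 8.2.1 names four COVID-19 symptoms and note c to Table 1 names nine, so chills, muscle pain, headache, loss of taste or smell and diarrhea could be taken as other symptoms and logged as adverse events. At stake is the only formal between-arm harm test that the text describes at the interim.

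**Working it through.** **The plan's own figures.** No power is stated for the safety test. The sample sizes in section 9.2 do reproduce: the two-sided Fisher exact test at 0.0492 has power 90.02% with 610 per arm (10% v 5%) and 90.04% with 172 per arm (30% v 15%). Dropout: 1220/0.9 = 1355.6, giving 1356; 344/0.9 = 382.2, giving 383.

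**Inputs from the plan.** Interim size per arm is 1356/4 = 339 (A) and 383/4 = 95.75, taken as 96 (B), together 435. Infection rates c are those above. The level is 0.0054, taken as two-sided (z = 2.782).

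**Assumptions the plan does not give.** The non-COVID event risk b in each arm; the share s of infections recorded as a safety event, equal in both arms; independence of the two kinds of event; and pooling of the cohorts. Section 2.2 notes that infection may be asymptomatic, so s is below 1.

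**Formulas.** Event risk per arm and cohort = 1 − (1 − b)(1 − s·c), averaged with weights 339 and 96. Power = Φ{[(p_T − p_C) − 2.782·se0]/se1}, where se0 uses the pooled proportion and se1 the two separate ones.

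**Worked case**, b = 10% v 20%, s = 0.2:
- Placebo: A 1 − 0.9 × 0.98 = 11.8%; B 1 − 0.9 × 0.94 = 15.4%; pooled 12.59%.
- Drug: A 1 − 0.8 × 0.99 = 20.8%; B 1 − 0.8 × 0.97 = 22.4%; pooled 21.15%.
- se0 = 0.0254, se1 = 0.0252, so power = Φ[(0.0856 − 0.0706)/0.0252] = 72%.

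**Results, pooled, efficacy as planned**

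| Non-COVID risk, placebo v drug | s = 0 | 0.05 | 0.1 | 0.2 | 0.3 | 0.6 |
|---|---|---|---|---|---|---|
| 10% v 20% | 91% | 88% | 83% | 72% | 60% | 24% |
| 5% v 10% | 51% | 40% | 30% | 16% | 8% | 0.6% |
| 20% v 40% | ~100% | ~100% | ~100% | ~100% | ~100% | 98% |
| 1% v 5% (serious) | 75% | 55% | 36% | 14% | – | – |

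For serious events a small s is just as compatible with the text: at 1% v 5%, s = 0.01 gives 71% and s = 0.02 gives 67%. If the drug has no efficacy, only dilution remains: 10% v 20% goes from 91% to 88% at s = 0.1.

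**Without pooling.** The interim is triggered within each cohort, so 435 per arm may never be the number analysed. Cohort A alone (339 per arm), 10% v 20%: 81% at s = 0, 73.5% at s = 0.1, 32% at s = 0.6. Cohort B alone (96 per arm) has 20% power at 10% v 20% and 12% at 1% v 5% even with COVID-19 excluded, so exclusion would not rescue it.

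**Cost of excluding COVID-19 events.** Suppose there is no toxicity, a 10% background risk in both arms, and half of infected participants' unrelated events are dropped because they fall near a positive test. Pooled infection is (339 × 10% + 96 × 30%)/435 = 14.4% on placebo and 7.2% on drug. The retained rates are 10% × (1 − 0.144 × 0.5) = 9.3% v 10% × (1 − 0.072 × 0.5) = 9.6%. The chance of a false stop rises from 0.27% to 0.47%.

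**The case for a change.** The strongest case for a change is that a rule that stops enrolment needs a defined variable, and that defining it after seeing data by arm would undermine it. Attribution-based holds depend on judging single cases; a between-arm test exists to find excesses that such judgement misses. Counting COVID-19 events lowers power in every scenario tried, even with no efficacy, and a clarification costs only wording.

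The direction of the effect stands, and so does the point that the definition must be settled before the interim. The practical weight is less. In the serious-event case, 5% of 435 is about 22 drug-arm participants against about 4 on placebo. Section 8.3.1 holds enrolment and convenes the SRC after any serious event judged at least possibly related, and section 8.3.3 has the study chair review events weekly. Harm on that scale would probably reach the SRC before the interim unless nearly every event were judged unlikely or unrelated. The SRC also reviews interim results and overall risk and benefit, so a disease benefit and a toxicity excess would come before the same body.

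The leak through the symptom lists is an inference. Section 8.2.1 takes its time points from the schedule whose note lists nine symptoms, and section 8.2.2 tracks a symptom only if it is an adverse event. Four against nine is a list that was not harmonised, a clerical slip.

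**Conclusion.** No change to the plan follows. Section 9.4 does leave its safety outcome undefined, but section 9.3 assigns analysis detail to a SAP, and event set, grade, unit and test are the detail a SAP carries. Table 1, section 8.2.1 and section 8.3.2 already point an analyst towards keeping the COVID-19 outcome separate; the broad definition in section 8.3 pulls the other way, so inclusion is possible but not established.

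If COVID-19 events were counted, the loss of power would run from negligible (20% v 40%, or 75% to 71% for serious events at s = 0.01) to severe (91% to 24% at 10% v 20%, s = 0.6). That range rests on background rates, a recording share, independence and pooling, none of which the documents give, so it cannot fix the seriousness of the point.

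Excluding COVID-19 events is a trade-off. It conditions on something that happens after randomisation and is expected twice as often on placebo, it can discard drug-caused events in infected participants, and in the illustration it nearly doubles the false-stop chance. An all-cause randomised comparison, read beside efficacy by the SRC, is a defensible default.

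### The interim safety rule in 9.4 describes a cohort-level safety comparison only after a significant overall test, which dilutes an excess confined to Cohort B

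*Combined protocol and SAP*

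**What the plan says.** Section 9.4 sets the interim look to be "performed when 50% of subjects, within their respective cohort, complete their 35 day follow-up". The safety step then reads "Overall safety will be analyzed first, and if safety outcomes are statistically higher in the treatment group" (at 0.0054), "enrollment will be stopped, participants will be unblinded and each cohort will be analyzed independently". If safety is not found to be compromised, the study may resume after the Safety Review Committee (SRC) has reviewed and recommended. No cohort-level safety comparison is described for that branch. Efficacy is handled differently in the same section: a significant result stops the cohort in which it occurred.

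Section 9.2 gives the sizes. For Cohort A, "the total sample size is 1356 patients (610 patients are needed in each arm + 10% dropout = 1356 total patients"; for Cohort B, "the total sample size is 383 patients (172 patients are needed in each arm + 10% dropout = 383 total patients". Section 9.3 names Fisher's exact test for infection status but only non-parametric methods for adverse events. The documents do not define overall, the safety outcome used at the look, the test applied to it or its sidedness.

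Two other sections bear on interim safety. Section 8.3.1 holds enrollment and convenes the SRC for any SAE, any cardiac AE of grade 2 or above, or any AE of grade 3 or above, if judged possibly, probably or definitely related to the intervention. Section 8.3.3 provides SRC meetings (monthly at first), weekly review of cumulative AEs and SAEs by the Study Chair, and SRC review of interim results.

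**The concern.** Cohort analyses follow the overall test as its consequence, so overall most naturally means the two cohorts combined. Read that way, benefit is judged cohort by cohort, while harm must first show up in a pool where Cohort A outnumbers Cohort B by about 3.5 to 1 (1356/383).

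Cohort B is selected in the Synopsis on age and comorbidity, including heart failure, cardiovascular disease and age 80 and above. The drug information in Appendix C says clinical studies had too few people aged 65 and over to tell whether they respond differently. An excess concentrated in Cohort B is therefore plausible, though nothing in the documents shows that it would occur. If it did, the pooled test could be non-significant, and the written rule would call for no between-arm look at Cohort B.

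**Working it through.** **Inputs from the documents.** Interim level 0.0054 and a look at 50% of each cohort (9.4); 1356 and 383 participants (9.2); 1:1 allocation in each cohort (6.1).

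**Assumptions.** All safety event rates are mine, because the documents give none. I treat the safety outcome as binary and use a two-sided Fisher's exact test, counted only when the hydroxychloroquine arm is higher. Both cohorts are taken at their halfway point. The pooled test is a simple pooled table. All probabilities are exact sums over the binomial distributions.

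**The plan's own figures.** The stated sizes reproduce. Exact power of two-sided Fisher at 0.0492 is 90.0% for 5% against 10% with 610 per arm, and 90.0% for 15% against 30% with 172 per arm. Dropout: 1220/0.9 = 1355.6, giving 1356; 344/0.9 = 382.2, giving 383. The plan states no power for the safety rule.

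**Numbers at the look.** Cohort A: 1356/2 = 678, or 339 per arm. Cohort B: 383/2 = 191.5, or about 96 per arm. Pooled: 339 + 96 = 435 per arm. Cohort B's share: 96/435 = 22%.

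**Dilution.** If the excess is in B only, pooled difference = (96/435) × difference in B. For 5% against 20% in B and 5% in both arms of A, the pooled treated rate is (339 × 0.05 + 96 × 0.20)/435 = 36.15/435 = 8.3%, against 5.0%. A 15-point difference becomes 3.3 points.

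**Probability of a safety signal at 0.0054** (control against treated):

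| Cohort A | Cohort B | Pooled | B alone |
|---|---|---|---|
| 5% v 5% | 5% v 20% | 16.8% | 61.3% |
| 2% v 2% | 2% v 15% | 26.6% | 68.4% |
| 10% v 10% | 10% v 30% | 18.4% | 72.9% |
| 5% v 5% | 5% v 15% | 5.8% | 26.1% |
| 1% v 1% | 1% v 5% | 1.9% | 2.3% |
| 5% v 8% | 5% v 20% | 59.1% | 61.3% |
| 5% v 10% | 5% v 20% | 83.2% | 61.3% |
| 5% v 12% | 5% v 12% | 80.6% | 10.5% |

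In the first four rows, harm is confined to B and pooling loses much of the power. In the fifth, events are rare and neither test helps. In the last three, A shares some excess and pooling does about as well or better.

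**Timing.** The looks are set by cohort, so Cohort A may not be at its halfway point when Cohort B is. For 5% against 20% in B alone, pooled power is 38.8% if A has 85 per arm at that time and 8.8% if A has all 678 per arm, against 61.3% in B alone.

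**False signals.** With no true effect, the chance of a false signal in Cohort B alone at 0.0054 is 0.08% at a 5% event rate and 0.17% at 20%.

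**The case against.** The strongest reply is that the formal test is not the trial's only protection. One related SAE, related grade 3 or higher AE or related grade 2 or higher cardiac AE in Cohort B triggers a hold under 8.3.1, whatever the pooled test shows, and the reviews in 8.3.3 run throughout. This stands, and it limits the point. A reader might infer that harm in Cohort B would usually be missed, or that Cohort B would simply keep enrolling. The documents do not support either: the low power belongs to one test under assumed rates, and resumption after a non-significant result requires SRC review. Nothing in 9.4 bars the SRC from seeing safety by cohort. What these safeguards leave open is narrower. The holds depend on attribution of individual events, so they do not reach a between-arm excess of lower-grade non-cardiac events, or of events judged unlikely or unrelated. Section 8.3.3 specifies no between-arm comparison by cohort.

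Second, both cohorts receive the same drug and dose, so some excess in Cohort A is plausible, and then pooling is a sound choice. This also stands. It is a reason to keep the pooled test rather than replace it.

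Third, a Cohort B test at 0.0054 has limited power itself: 26.1% for 5% against 15%. For smaller or rarer excesses, the size of Cohort B and the strict level matter as well as the dilution.

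Fourth, overall is undefined and sits beside per-cohort timing, so it could mean all safety outcomes within a cohort. That reading is possible but fits poorly with the cohort analyses that follow it. Either way the text needs to say which is meant.

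**Conclusion.** The point holds as a weakness in the written interim safety rule. On the pooled reading, the only formal between-arm interim safety comparison in the documents has low power for a moderately common excess confined to Cohort B: 17% against 61% for 5% against 20%, and 6% against 26% for 5% against 15%. These figures rest on assumed event rates, a binary outcome, Fisher's test, no excess in Cohort A and both cohorts at half. The advantage of the separate test nearly vanishes with a modest excess in A (59% against 61%) and reverses when harm is shared equally (81% against 11% for 5% against 12% in both). The practical gap is lower-grade or unattributed excesses in Cohort B. It should be corrected, but it does not show that the trial's safety oversight as a whole is inadequate.

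**What to change.** Amend 9.4 to:

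- define overall, the safety outcome or outcomes compared at the look, the test and its sidedness;
- keep the pooled safety comparison, stratified by cohort;
- state that safety is also compared between arms within each cohort at that cohort's look, whatever the pooled result, and that any cohort-specific signal is referred to the SRC.

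Stratifying alone is not enough: it adjusts for different background rates but still averages over both cohorts, so the within-cohort comparison is needed too.

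The cost is a few sentences in 9.4, one more table per look, and a slightly higher chance of a false signal: about 0.1% in Cohort B at the 0.0054 level with a 5% event rate. Because the pooled test stays, no power is given up for harm shared by both cohorts.
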